Transfusion will be based on standard of care utilizing clinical criteria of hemodynamics (noninvasive blood pressure, heart rate, arterial line if deemed clinically useful) and coagulation labs (PT, aPTT, fibrinogen, complete blood count, red top test) in both groups. In addition to standard of care, additional ROTEM blood assays will be performed at any time routine coagulation labs are sent. Providers in the control group will be blinded to ROTEM results. Providers in the ROTEM group will receive real-time ROTEM results and a previously validated ROTEM-based transfusion algorithm for PPH (Mallaiah et al 2015). The investigator will quantitatively measure blood loss during the vaginal or cesarean delivery using a previously validated method (Triton System, Gauss Surgical Inc. Los Altos, CA). The total intravenous fluids given from start to conclusion of the study period will be recorded. The use of vasopressors, uterotonic agents, and antiemetic agents will be recorded.

Study Endpoints

Early Endpoints

Two definitions of early endpoints will be utilized:

1. Subject decision for withdrawal from participation at any time.
2. Any operative or medical condition changes prior to or during the entire study period deemed unacceptable by the obstetrician, anesthesiologist, or physician investigator.

Primary Endpoint

1. Number of blood products transfused, t_0 = diagnosis of PPH by criteria defined above; $t_{\text{final}} = 48\text{h}$ after onset of PPH.

Secondary Endpoints

1. ROTEM values drawn at the time of the last blood sampling within 4 hours from leaving the operating room or within 4 hours from the last blood transfusion, whichever occurs later.
2. Intraoperative blood loss (visual estimate in suction canister and sponges, EBL, and pre- vs post-delivery hemoglobin values).

Maternal morbidity: admission to the intensive care unit postpartum, need for additional postoperative procedures for bleeding, hysterectomy, postoperative infection, transfusion reaction, acute kidney injury, hypovolemic shock, vasopressor requirement, or mortality. Patient records at the 6-week postpartum visit will be reviewed for any incidence of delayed hemorrhage after hospital discharge.

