All clinical and other data obtained during this study will be considered confidential. Procedures to limit access to subject charts and information from the study will be in place. The names of study participants will be known only to the investigators. No information regarding the identity of individual subjects will be utilized for publications.

Outcomes considered serious adverse events including hemodynamic instability requiring epinephrine or norepinephrine or resulting in loss of consciousness or cardiovascular collapse, or allergic or anaphylactic reactions may all fit the criteria for withdrawal from the study. Each of these events will warrant an evaluation by the PI; please see “monitoring section” below.

Subject Costs

There will be no costs to the subjects related to the conduct of this study, as there are no additional medications or tests that are not already the routine standard of care at Brigham and Women’s Hospital. ROTEM testing used in the study group will be performed by qualified obstetric anesthesiology physicians under the supervision of a certified lab director, with funding from the department of Obstetrics and Gynecology. Otherwise, subjects and/or their insurance companies will be responsible for the routine medical and surgical procedures and care associated with their cesarean delivery or vaginal delivery and hospitalization.

BIOSTATISTICAL ANALYSIS

ROTEM values between the control and ROTEM groups will be compared as quantitative outcomes against pre-established ranges for each value in pregnancy and choice of product transfused with or without the ROTEM protocol will be compared.

Sample size calculations for the primary outcome of number of blood products transfused is based on a surrogate finding of reduction in transfused products in a matched study population that was demonstrable using 50 subjects per group). We anticipate that by recruiting the same number of patients as in this previous study (100 patients total), we will reproduce the effects of reducing blood product transfusion. A group size of $n = 50$ will give a power of 80% ($\beta = 0.2$) based on a 5% significance ($\alpha = 0.05$); 100 subjects per group will be recruited with the goal of completing 50 subjects in the control group and 50 subjects in the ROTEM group.

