Data will be analyzed using one-way analysis of variance and Kruskal-Wallis tests as appropriate. Analysis of variance will be used to compare intergroup demographic data, estimated blood loss (EBL), ROTEM values, and hemoglobin values. All statistical analyses will be performed using Statview v 5.0 for Macintosh. A P value < 0.05 will be considered significant and all data will be reported as mean \pm standard deviation.

Note: the study was stopped prior to our goal enrollment of 100 patients (N = 50 per group). Our total recruitment was N = 49; 26 control, 23 ROTEM due to slower than anticipated recruitment (3 years and 1 month). The decision to stop the trial early was not out of concern for patient safety or adverse events. We are aware that trials stopped earlier than anticipated may dramatically overestimate the effect of an intervention. However, given our lack of impact on our primary outcome in the intervention group we can infer that additional recruitment would yield results of the same clinical outcome (no effect).

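### One P < 0.05 rule covers every analysis, and some 7 to 15 or more secondary comparisons have neither exploratory status nor multiplicity control

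*Combined protocol and SAP*

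**What the plan says.** The last paragraph on methods under BIOSTATISTICAL ANALYSIS states: "A P value < 0.05 will be considered significant". The sentence follows one about all statistical analyses and carries no restriction.

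The Study Endpoints section separates a Primary Endpoint, "Number of blood products transfused" (counted to 48 hours), from the Secondary Endpoints. The secondaries are ROTEM values, intraoperative blood loss (visual estimate, EBL and hemoglobin change) and maternal morbidity: "admission to the intensive care unit postpartum, need for additional postoperative procedures for bleeding, hysterectomy, postoperative infection, transfusion reaction, acute kidney injury", followed by hypovolemic shock, vasopressor need and death. Delayed hemorrhage is then sought at the 6-week record review.

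BIOSTATISTICAL ANALYSIS adds that ROTEM values will be "compared as quantitative outcomes against pre-established ranges for each value in pregnancy", and that product choice will be compared between groups. It also says: "Analysis of variance will be used to compare intergroup demographic data", together with EBL, ROTEM values and hemoglobin. The tests named are one-way ANOVA and Kruskal-Wallis. No test is named for binary outcomes, and the text does not say whether morbidity is one composite or several items.

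The closing note reports 49 patients recruited (26 control, 23 ROTEM) and no effect on the primary outcome.

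**The concern.** Followed literally, the rule lets any secondary comparison that falls below 0.05 be declared significant, however many were made. This matters more once the primary is reported as null, because the secondaries are then the only place where a difference could still be claimed. At 26 and 23 patients, a result that just crosses 0.05 also tends to overstate the effect behind it.

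The demographic tests are a lesser matter. Under sound randomization a baseline difference arises by chance, so a P value for it answers no useful question. These tests are not outcome claims and are left out of the counts below.

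**Working it through.** **The plan's own figure.** The plan states no familywise error rate. Its only error-rate figures, alpha 0.05 and the statement that 50 per group "will give a power of 80" percent, belong to the primary endpoint. The 80% cannot be reproduced: no effect size or SD is given, only a "surrogate finding of reduction in transfused products in a matched study population that was demonstrable using 50 subjects per group". Solved backwards, 50 per group implies a standardized difference of (1.960 + 0.842) × √(2/50) = 0.56 two-sided. This confirms that the sample size rests on one primary test and covers no secondary.

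**Count of secondary comparisons** (Study Endpoints and BIOSTATISTICAL ANALYSIS)

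| Item | Morbidity as composite | Items one by one |
|---|---|---|
| ROTEM values, counted once | 1 | 1 |
| Product choice, counted once | 1 | 1 |
| Blood loss: visual estimate, EBL, hemoglobin | 3 | 3 |
| Maternal morbidity | 1 | 9 |
| Delayed hemorrhage | 1 | 1 |
| Total | 7 | 15 |

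If the visual estimate is the EBL, each total falls by one. The phrase "pre-established ranges for each value in pregnancy" implies several ROTEM values, which would raise the totals, but no number is given.

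**Independent tests, each at full 5% size, all nulls true.** P(at least one P < 0.05) = 1 − 0.95^k.

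- k = 4 (only the secondaries that BIOSTATISTICAL ANALYSIS expressly says will be compared: ROTEM values, product choice, EBL, hemoglobin): 19%
- k = 6: 26%
- k = 7: 30%
- k = 14: 51%
- k = 15: 54%
- k = 20 (if more ROTEM values or product types are tested): 64%

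**Allowing for rare binary outcomes.** Ten of the 15 are binary (nine morbidity items and delayed hemorrhage), and a test on rare events does not reach 5% size. The exact size s at 26 vs 23 was enumerated for assumed event rates; the documents give none. The family figure is 1 − 0.95^5 × (1 − s)^10, with 0.95^5 = 0.7738.

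| Assumed event rate | s, Fisher | s, Kruskal-Wallis | Family, Fisher | Family, Kruskal-Wallis |
|---|---|---|---|---|
| 1% | 0.0001 | 0.0001 | 23% | 23% |
| 5% | 0.0076 | 0.0098 | 28% | 30% |
| 10% | 0.0214 | 0.0310 | 38% | 44% |

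ANOVA on a 0/1 outcome has the same size as Kruskal-Wallis at these rates. The choice of test matters. An uncorrected chi-square test, which the plan does not name, has s = 0.0191 at a 5% rate and 0.0441 at 10%, so the family figures are 1 − 0.7738 × 0.9809^10 = 36% and 1 − 0.7738 × 0.9559^10 = 51%. At the planned 50 per group, Kruskal-Wallis would give 24%, 50% and 53% at rates of 1%, 5% and 10%, and Fisher 23%, 28% and 35%.

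**Allowing for correlation.** Simulation of equally correlated normal statistics at full 5% size (400,000 draws):

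- 15 tests: 46% at correlation 0.3 and 36% at 0.5
- 7 tests: 27% at correlation 0.3 and 23% at 0.5

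**The case against.** The strongest reply is that the plan already has the structure that matters: one primary endpoint under its own heading, with alpha, power and sample size attached to it alone. A reader might infer from the single threshold that nothing separates the primary from the rest, or that its error rate is inflated. The documents support neither. What is missing is the inferential status of the secondaries.

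A reader might also count at least 16 outcome comparisons, including the primary, and call a false secondary finding close to a coin flip. Sixteen is not a minimum: it needs the visual estimate and EBL to be separate outcomes and each morbidity item to be tested alone. The morbidity list ends in an 'or' and reads equally well as a composite. The coin-flip figure also needs independence and full 5% size, which rare events and related outcomes do not give. Figures near or above one half without any morbidity item need assumed numbers of ROTEM values and product types treated as independent. That is implausible, since ROTEM values come from the same blood sample and product types are parts of the primary count.

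Finally, a reader might infer that a positive message will be drawn from a secondary. The closing note claims no such benefit and concludes only that there was no effect. The rule leaves room for a chance claim; the documents do not show that one was made.

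These objections reduce the size of the problem. They do not supply an exploratory label or any multiplicity control, and the document contains neither.

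**Conclusion.** The point holds as a gap in the status of the secondary analyses. The 30% to 54% range for 7 to 15 tests assumes that all nulls are true and that the tests are independent at full 5% size. The 23% to 44% range for 15 tests assumes event rates of 1% to 10%, Fisher or Kruskal-Wallis on the binary items, and 26 vs 23 patients. Positive correlation lowers both ranges; separate tests of several ROTEM values or product types raise them. Even 23% is more than four times the nominal 5%. The spread reflects what the plan leaves open: how many ROTEM and product comparisons there are, whether morbidity is a composite, and how binary outcomes are tested. The primary result and its 5% error are unaffected, and removing the demographic P values changes no outcome result.

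**What to change.** Replace the threshold sentence with: 'The primary comparison is tested at two-sided 0.05. Secondary endpoints are exploratory and are reported as between-group differences with 95% confidence intervals, without claims of significance.' Show demographics descriptively, without P values. State also whether morbidity is reported as a composite or item by item.

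Recruitment has ended and the primary result is known, so declare the change as a post hoc reporting rule. It needs no new data.

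The cost is that an unadjusted secondary P < 0.05 can no longer be called significant. A mandatory Holm adjustment over all secondaries is not proposed: it would make rare harms harder to flag, a debatable trade in a trial of 49 patients.

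### Reporting all data as mean ± SD does not suit the yes/no morbidity outcomes, and no between-arm estimate or interval is planned to support the conclusion of no effect

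*Combined protocol and SAP*

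**What the plan says.** The last part of the section Biostatistical Analysis sets a single reporting format: "all data will be reported as mean" ± standard deviation. It carries no exception by type of variable.

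The data it covers are listed under Study Endpoints:

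- The primary endpoint is a count: "Number of blood products transfused", from diagnosis of postpartum hemorrhage to 48 hours after onset.
- Maternal morbidity is a list of yes/no items. It begins "Maternal morbidity: admission to the intensive care unit postpartum, need for additional postoperative procedures for bleeding, hysterectomy", continues with infection and transfusion reaction, and ends with "acute kidney injury, hypovolemic shock, vasopressor requirement, or mortality". That makes nine items.
- Records at the six-week visit "will be reviewed for any incidence of delayed hemorrhage after hospital discharge", which is one more yes/no outcome.

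On testing, the plan says: "Data will be analyzed using one-way analysis of variance and Kruskal-Wallis tests as appropriate". It then assigns variables: "Analysis of variance will be used to compare intergroup demographic data, estimated blood loss (EBL), ROTEM values, and hemoglobin values". Neither the product count nor morbidity is in that list. The only decision rule is "A P value < 0.05 will be considered significant". Percentages, medians, risk differences and confidence intervals are not mentioned anywhere.

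The closing note reports that recruitment stopped at 49 women (26 control, 23 ROTEM) instead of 100. From the lack of impact on the primary outcome, it infers that further recruitment would also have shown no effect.

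**The concern.** For a yes/no outcome, the SD is a function of the proportion and n, so printing it adds nothing. The reader wants the number of events, the denominator and a statement of what event rates remain plausible. The rule supplies none of these directly. Rare serious events in a small trial are where that matters most.

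For the product count, the mean is a legitimate summary. Mean ± SD alone, however, does not show how many women received nothing or whether a few heavily transfused women drive the mean. The plan allows a rank test where appropriate, so it foresees non-normal data for testing, but the reporting rule has no matching provision.

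The larger stake is the conclusion. A P value and two per-arm SDs do not tell a reader which effects the trial has ruled out. A claim of no effect from 49 women needs an estimate of the arm difference with an interval, and none is planned.

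**Working it through.** **Inputs from the documents.** Actual arms are 26 control and 23 ROTEM. The planned completers are 50 per arm, with 80% power and α = 0.05 (sidedness not stated; taken as two-sided). No effect size, mean or SD is given for the product count, and no results by outcome.

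**1. The plan's own figure.** The 50 per arm cannot be reproduced, because no effect size or SD is stated. It can be solved backwards for the standardized difference:

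d = (z₀.₉₇₅ + z₀.₈₀) × √(2/n) = (1.960 + 0.842) × √(2/50) = 2.802 × 0.200 = 0.56 SD.

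A t-test calculation gives 0.57, and a one-sided reading gives 0.50.

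**2. A yes/no item with no events.** All values are 0, so mean = 0 and SD = 0 at any n, and the rule prints 0 ± 0. The exact (Clopper-Pearson) two-sided 95% upper limit is 1 − 0.025^(1/n):

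| Arm | Prints as | Exact 95% upper limit |
|---|---|---|
| 0/23 (ROTEM) | 0 ± 0 | 14.8% |
| 0/26 (control) | 0 ± 0 | 13.2% |
| 0/50 (as planned) | 0 ± 0 | 7.1% |

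With no events in either arm, the Newcombe 95% interval for the risk difference (ROTEM minus control) uses the Wilson upper limits z²/(n + z²), with z² = 3.84:

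- 3.84/26.84 = 14.3% for n = 23.
- 3.84/29.84 = 12.9% for n = 26.

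The interval is therefore −12.9 to +14.3 percentage points.

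**3. A yes/no item with one event.** One event in 23 has mean 1/23 = 0.04 and SD 0.21. It should read 1/23 (4.3%), with an exact 95% interval of 0.1% to 21.9%.

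**4. The product count (assumed distributions).** Take a mean of 3. Under Poisson, SD = √3 = 1.7. Under a negative binomial with dispersion k, SD = √(3 + 9/k):

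| Distribution | SD | Mean − SD |
|---|---|---|
| Poisson | 1.7 | 1.3 |
| Negative binomial, k = 5 | 2.2 | 0.8 |
| Negative binomial, k = 1.0 | 3.5 | −0.5 |
| Negative binomial, k = 0.5 | 4.6 | −1.6 |

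The SD exceeds the mean when 3 + 9/k > 9, that is, when k < 1.5. Whether mean ± SD is an adequate summary therefore depends on a dispersion that the documents do not give.

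**5. Precision of the arm difference actually achieved.** The 95% half-width for a difference in means is

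t₀.₉₇₅,₄₇ × √(1/26 + 1/23) = 2.012 × 0.286 = 0.58 SD.

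At the planned 50 per arm it would have been 0.40 SD. The achieved half-width of 0.58 SD is slightly larger than the implied design effect on each reading in step 1 (0.50, 0.56 or 0.57 SD). Power for 0.56 SD at 26 versus 23 is about 50%.

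**The case against.** The strongest reply is that the format is awkward but loses no information. For a 0/1 item, mean × n gives the event count, so 0 ± 0 with n = 23 means exactly 0/23 and the 14.8% limit can be recovered. For the primary outcome, two means, two SDs and the arm sizes give a t interval. A descriptive format also does not forbid intervals. All of this is correct, and it limits the point: precision is left for the reader to work out, not destroyed. A plan should still not leave its effect estimates to its readers, least of all when it draws a conclusion that depends on them.

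A reader might infer more than the documents support:

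- **That the printed error bars would be wrong.** An SD is not a precision bar, so setting 0.04 ± 0.21 against a confidence interval does not show an incorrect one. A mean minus SD below zero is not an error either; for a count it signals skew.
- **That the product count is known to be skewed.** The documents give no distribution. Under Poisson with mean 3, mean ± SD is tolerable.
- **That a zero-event item was in fact reported as 0 ± 0.** No outcome results are given; this is only what the rule would print.
- **That the named tests are badly invalid for yes/no data.** Exact enumeration over event rates puts the highest type I error of analysis of variance at 5.2% for 26 versus 23, and that of both tests at 5.7% for 50 versus 50. The excess over 5% is small, and this point does not rest on it.

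**Conclusion.** The point holds as a fault in the reporting rule and in what the plan lets the trial conclude. Mean ± SD is the wrong format for ten yes/no outcomes (nine morbidity items and delayed hemorrhage). With no events it would show 0 ± 0 where rates up to 14.8% (0/23) or 13.2% (0/26) are compatible with the data. For the product count it may be inadequate as the only summary; that part is conditional on overdispersion.

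The most consequential gap is the missing between-arm interval. With a half-width of about 0.58 SD against an implied design effect of about 0.56 SD, an observed difference of zero would not exclude the effect that the trial was sized to find. The inference of no effect is thus not supported by anything the plan reports. This comparison assumes a two-sided α, an ordinary two-sample comparison of means, and that the planning SD and the observed SD are on the same scale. The margin is narrow, so the safe statement is that the design effect is not clearly excluded; it does not follow that an effect exists.

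The sample size, α and choice of tests are unaffected. This is a change that should be made, short of one that invalidates the design.

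**What to change.** Replace the reporting sentence in Biostatistical Analysis with wording to this effect:

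- *Yes/no outcomes: n/N (%) per arm, with the risk difference and a score (Newcombe) or exact 95% interval.*
- *Product count: mean (SD), median, quartiles and number untransfused per arm, with the between-arm difference in means and a t-based 95% interval.*
- *Blood loss, hemoglobin and ROTEM values: between-arm difference with 95% interval.*
- *Mean ± SD alone is used only for roughly symmetric baseline variables.*

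Reword the closing note so that the primary conclusion is stated from the interval for the product count: which differences the data exclude and which they do not.

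A t-based interval is adequate for the count at these arm sizes. In simulation under the negative binomial assumption above (mean 3, k = 0.5 and 1.0, 26 versus 23, no true difference), it covered about 95%.

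The cost is SAP wording and a small amount of table programming on data already held. The plan names a single statistics package; if that package does not produce score or exact intervals, a second tool should be named.

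### The early-stopping note turns an unquantified null at 49 of 100 planned patients into a finding of no effect; power for the effect implied by the sample size was about 49%

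*Combined protocol and SAP*

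**What the plan says.** The Primary Endpoint is a count: blood products transfused from the diagnosis of postpartum hemorrhage to 48 hours after onset.

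The Biostatistical Analysis section sizes the trial at 50 completers per group for 80% power at 5% significance. It states no effect size or SD. The basis is a "surrogate finding of reduction in transfused products in a matched study population", with the expectation that "we will reproduce the effects of reducing blood product transfusion". For the analysis it says "Data will be analyzed using one-way analysis of variance and Kruskal-Wallis tests as appropriate". For reporting it says "A P value < 0.05 will be considered significant and all data will be reported as mean" and standard deviation. It does not ask for a confidence interval.

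The note at the end of the section gives the outcome of recruitment: "Our total recruitment was N = 49; 26 control, 23 ROTEM due to slower than anticipated recruitment". It adds one caution, that "trials stopped earlier than anticipated may dramatically overestimate the effect of an intervention". Its premise for the next step is worded "given our lack of impact on our primary outcome in the intervention group". The conclusion drawn from that premise is that "we can infer that additional recruitment would yield results of the same clinical outcome (no effect").

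**The concern.** Two different claims are run together. One is a forecast: had the trial continued to 100 patients, the comparison would still not have been significant. The other is a conclusion about the intervention: it has no effect on transfusion. The first can be true while the second is false, because a small trial of a real effect can also be heading for non-significance.

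The caution in the note points the wrong way for a null result. It warns that early stopping can exaggerate an effect. The risk that goes with a null claim at half the planned size is a missed effect, and the note does not mention it.

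This is the only statement about the primary result in the supplied text. A reader could take it to mean that ROTEM-guided transfusion was shown not to change product use, when the trial's own sizing says 50 per group were needed to detect the reduction it expected.

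**Working it through.** **Inputs.** From the Biostatistical Analysis section: 50 per group, power 80%, α = 0.05 (sidedness not stated). From the note: 26 control and 23 ROTEM. Assumed: two-sided test, t-test (the same as one-way ANOVA with two groups), equal SDs, approximately normal outcome, all 49 patients analysed. I read the reported lack of impact as a non-significant comparison.

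**1. The plan's own figure.** The 80% cannot be reproduced, since no effect size or SD is given. It can only be inverted. With noncentrality d / √(1/n₁ + 1/n₂):
- At 50 vs 50, √(1/50 + 1/50) = 0.200. Solving for 80% power on 98 df gives d = 0.566 SD (noncentrality 0.566 / 0.200 = 2.83).

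**2. Power at the achieved size.**
- √(1/26 + 1/23) = 0.286; noncentrality 0.566 / 0.286 = 1.98; critical t on 47 df = 2.012.
- Power = 0.491, against the planned 0.80.

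| Variation | Power at 26 vs 23 |
|---|---|
| Normal approximation, d = 0.560 | 49.9% |
| One-sided 5%, d = 0.501 | 53.2% |
| True effect 0.4 SD, two-sided | 28% |
| True effect 0.8 SD, two-sided | 78% |
| Assumed negative binomial counts (control means 2, 4, 8; dispersion 0.5, 1, 2), rate ratio set for about 80% at 50 vs 50 | 42–48% (t-test), 48–50% (Kruskal-Wallis) |

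At 26 vs 23, 80% power needs an effect of 0.82 SD.

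**3. What an interval could exclude.** Two-sided 95% half-width:
- Achieved: 2.012 × 0.286 = 0.576 SD.
- Planned: 0.397 SD.

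From an estimate of exactly zero, the achieved interval includes the design effect by 0.576 − 0.566 = 0.01 SD. The one-sided 95% bound from zero is 0.480 SD, which excludes the one-sided design effect of 0.501 SD. An estimate near zero is therefore a borderline case, and the actual estimate decides it.

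**4. Does the forecast imply no effect?** The information fraction is t = (0.200 / 0.286)² = 0.488 and the drift is θ = 0.566 / 0.200 = 2.83 under the design effect. The chance of significance at 100 patients given current z is

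1 − Φ[(1.96 − z√t − θ(1 − t)) / √(1 − t)],

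with the opposite tail added where it matters. The observed z is not given, so the values below are assumptions.

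| z now | Under the design effect | Under no effect |
|---|---|---|
| −0.5 | 11% | not computed |
| 0 | 24% | 0.6% |
| 0.5 | 41% | 1.3% |
| 1 | 60% | 4% |

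At z = 0 under the design effect: (1.96 − 0 − 1.45) / 0.715 = 0.72, and 1 − Φ(0.72) ≈ 0.24. Non-significance at 100 patients is then likely under both hypotheses (76% and 99.4%), so a correct forecast of it does not show that there is no effect.

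**5. How often a non-significant result excludes the design effect.** In 2,000,000 simulated trials at 26 vs 23, the 95% interval of a non-significant result excluded 0.566 SD 49% of the time when the true effect was zero, and 5% when it was 0.566 SD. The data may or may not exclude the planned effect; non-significance alone does not say.

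**The case against.** The sentence can be read as a forecast of the trial's result, with the parenthesis only labelling that result. If so, the fault is one ambiguous phrase. That reading is available, and the forecast may well be fair. But the wording also supports the stronger reading, and the remedy on either reading is to say which is meant.

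The data may in fact exclude the planned effect, especially if the estimate leaned towards control: at an assumed z of −0.5, the chance of later significance is only 11% even under the design effect. This stands. The point here is that the inference is not supported in the text, not that it is known to be false.

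A protocol with a short closing note is not where results are normally reported, and an interval may exist elsewhere. That is fair, but the note itself draws a conclusion about the result and should carry what the conclusion rests on.

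The 0.57 SD is inferred from an unexplained 80%, and once data exist the interval matters more than power. Both are true. The figure applies the plan's own target to the achieved size rather than computing power from the observed effect, and the fix relies on the interval. The section also speaks of recruiting 100 per group. If that were the powered size, power at 26 vs 23 would be lower still, 28% (normal approximation).

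Nothing is claimed about a futility rule. The documents refer to a monitoring section that was not supplied, and the stated reason for stopping is recruitment.

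**Conclusion.** The concern holds. The note infers no effect, and extends it to patients never enrolled, from an unquantified null in 49 of 100 planned patients. On the stated assumptions, power for the effect implied by the sample size fell from 80% to about 49% two-sided (53% one-sided; 42–50% with assumed skewed counts), and the 95% half-width of about 0.58 SD is roughly the size of that effect. The exact power depends on the back-solved effect. The central fault does not: non-significance, and a forecast of more of it, do not establish absence of effect. Whether the data exclude the planned effect depends on an estimate that the text does not give. The decision to stop is not in question.

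**What to change.** Delete the no-effect parenthesis and the claim that it can be inferred for patients who were not enrolled. The forecast may stay if it is worded as one about statistical significance and given with the estimate behind it. If the parenthesis meant only the same non-significant result, say so. Beside the existing caution on overestimation, add for example:

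> The trial stopped at 49 of 100 planned patients because of slow recruitment. Power for the effect implied by the sample-size calculation fell from the planned 80% to roughly 50% (back-solved; t-test, equal SDs, approximately normal outcome). The between-group difference in blood products transfused was [x] (95% CI [a] to [b]). The result is inconclusive for any effect inside this interval.

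Add that a real effect of the planned size may have been missed only if the interval does not exclude it. If a relevant difference is used as a yardstick, take it from the earlier study used for sizing and label it post hoc.

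Use an interval suited to a skewed count, for example a bootstrap interval with a Welch interval as a check. On the assumed count distributions at 26 vs 23, nominal 95% coverage was 0.92–0.94 for the percentile bootstrap and 0.94–0.96 for Welch, so Welch is the safer choice if only one is shown.

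The cost is a short rewording and one interval from data already collected. The planned means and SDs, with the group sizes, already allow the Welch interval; the bootstrap needs the patient-level counts. The conclusion becomes less definite.
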